10.4.5 Adherence and Retention Analyses

As all treatments in this study are directly provided by a clinician to the patient, there is no measure of adherence to the protocol. However, we will provide descriptive statistical information of the number of patients lost to follow-up or changed schools within the study. Where possible, we will attempt to ascertain the reasons for discontinuation of the study, however in our experience in pragmatic school-based trials this usually stems from participants leaving the school district.

10.4.6 Baseline Descriptive Statistics

Intervention groups will be compared on standard baseline characteristics and prognostic indicators. Full description is included in the Study SAP.

10.4.7 Planned Interim Analysis

BASICS is a sequential, multiple-assignment, randomized trial. By definition this includes interim analysis for treatment responsiveness, followed by second-stage randomization. Full description is included in the Study SAP.

10.4.7.1 Safety Review

As all treatments are standard of care, there are no safety endpoints beyond adverse event reporting.

10.4.7.2 Efficacy Review

Efficacy endpoints include treatment responsiveness after stage-1 and stage-2 randomization phases. Full description is included in the Study SAP.

10.4.8 Additional Sub-Group Analyses

Planned subgroup analyses by select tailoring variables are included in the study SAP.

10.4.9 Multiple Comparison/Multiplicity

Despite multiple comparisons arising from multiple DTRs in a SMART trial, adjustment is often not performed in the literature. Multiple comparisons are minimized in listed objectives (see SAP), but we will also include methods to account for multiplicity including Benjamini & Hochberg and Multiple. Further description is included in the Study SAP.

10.4.10 Tabulation of Individual Response Data

Individual patient descriptive data will be summarized overall, by subgroup, and by observation.

10.4.11 Exploratory Analyses

SMART trials support specific hypothesis-generating analyses using Q-learning, which is described in the study SAP.

10.5 Sample Size

Sample size calculations for Objective 1 are computed for the main effects of the specified experimental design, including the main effects for first-stage treatment (A+B+C vs D+E+F) and the main effects for second-stage treatment in nonresponders (B+E vs C+F). These main effects are equivalent to a longitudinal comparison of two parallel groups in a randomized trial [45]. We assume a within-person correlation of 0.5, a study drop-out rate of 10% (with the difference offset by newly enrolled children each year), a desired power of 0.85, and an alpha of 0.05. This yields a total sample size of 122 for a medium effect size (Cohen's $d=0.5$). As a result, our anticipated

sample size is sufficient for even small to medium effects at acceptable power levels. We subsequently propose sampling more subjects to support investigation of effect modifiers or subgroup comparisons (e.g., A+B, A+C, D+E). For second-stage treatment main effects, additional considerations are needed for the rate of nonresponse [45]. We assume nonresponse rates are equal across first-stage treatment assignments, and further assume an average nonresponse rate of 30% (as informed by prior studies). This yields a total N of $122/0.3 = 406$, or N=203 for first-stage treatment groups and 101 in each nonresponse group (B+E and C+F).

For Objective 2, we estimate power based on the Multiple Comparisons with the Best (MCB) methodology for comparing our embedded DTRs while accounting for multiple comparisons, thereby increasing power [46]. We assume a type 1 error rate, now viewed as the probability of excluding the best DTR from the set of all DTRs, of 5%. We estimate the expected power given our anticipated final sample size assuming the same 10% yearly dropout rate (N=840) for four DTRs, with a minimum effect size of 0.1: $Power_{\alpha,n}(\Sigma, \Delta, \Delta_{min}) \geq 1 - \beta$. We assume the most conservative case as possible by setting all other DTRs to be the minimum detectable effect size away, compared to DTR(1) ($\Delta_i = \Delta_{min}$). We also assume that correlations between DTRs are equal, in keeping with recommendations. This yields a power of >99%, and the study is well powered even for exceedingly small effect size differences. Finally, as optimization using Q-learning is considered hypothesis generating in the SMART framework, we do not estimate power for this analysis.

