Subgroup Size and Interventions

Subgroup A	N = 420	Silver diamine fluoride (single application)
Subgroup B	N = 90	Silver diamine fluoride (initial treatment) followed by SDF reapplication plus FV plus electronic toothbrushing
Subgroup C	N = 90	Silver diamine fluoride (initial treatment) followed by GIC sealant application and silver modified atraumatic restorations
Subgroup D	N = 420	GIC sealants (single application)
Subgroup E	N = 90	GIC sealants (reapplication, as ART) followed by FV plus electronic toothbrushing
Subgroup F	N = 90	Add SDF as silver modified atraumatic restorative treatment

1 Key Roles

Principal Investigator

[name] [name], MPH; Associate Professor
New York University
[name]
[name]
[contact]
[contact]

Clinical Director (Sub-Investigator)

[name] [name], MPH; Research Scientist
New York University
[name]
[name]
[contact]
[contact]

Research Scientist (Sub-Investigator)

[name]; Assistant Professor
New York University
[name]
[name]
[contact]
[contact]

Site PI

To Be Determined

NIH Program Director

[name]
Supervisory Team Lead, Integrative Biological and Environmental Sciences
National Institute on Minority Health and Health Disparities
[name]
[contact]
[contact]

2 Introduction, Background Information and Scientific Rationale

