10.4 Description of Statistical Methods

10.4.1

General Approach

BASICS is a phase-III Sequential, Multiple Assignment, Randomized Trial (SMART) (described fully in the Schematic of Study Design). Descriptive statistics will use percentages and counts for persons with dichotomous outcomes and means/standard deviations for continuous outcomes. For inferential tests, the p-value used for statistical significance (Type 1 error) is 0.05, and all tests are two-tailed.

10.4.2

Analysis of the Primary Efficacy Endpoint(s)

The primary efficacy endpoints include the best initial treatment for dental caries and the best treatment sequence for nonresponders. This is equivalent to the main effect of the first-stage treatment and additional clinically-relevant contrasts (see Statistical Analysis Plan for further description). Data will be analyzed according to intent to treat. The main effects will be assessed using generalized linear mixed logistic regression (for presence/absence of dental caries and presence/absence of treatment nonresponse) and negative binomial regression (for caries incidence). Predictors include semester of entry, the interaction between semester and treatment trajectory, and any relevant demographic variables. Any instance of missing data will be accounted for using time-ordered nested conditional imputation.

10.4.3

Analysis of the Secondary Endpoint(s)

Secondary endpoints in BASICS include the best dynamic treatment regime, the optimal adaptive intervention, and costs of adaptive interventions. Analysis for the best adaptive intervention will utilize weighting and replication and other methods (see Statistical Analysis Plan). Analyses for identifying the optimal adaptive intervention will use Q-Learning (see SAP).

For cost analyses, we will quantify the economic costs of dynamic treatment regimes in school-based caries prevention will using microcosting in tandem with time studies. We will take a bottom-up microcosting approach to data collection. The bottom-up approach to microcosting is characterized by quantifying resource utilization for each cost item, and then aggregating to the individual or system-level, as opposed to assessing system costs and then allocating to individual cost items (top-down approach).⁷³ This approach is more accurate for labor-intensive services than microcosting with a top-down approach.⁷⁴⁻⁷⁶ We will use the following tools to capture costs:

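### Protocol Section 10.5 gives 101 nonresponders in each second-stage group at a total of 406, but its own 30% nonresponse rate gives 61

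*Protocol*

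**What the plan says.** All of the derivation is in Protocol Section 10.5. The design inputs are "a desired power of 0.85, and an alpha of 0.05", and Section 10.4.1 adds that "all tests are two-tailed". With a within-person correlation of 0.5 and 10% dropout, Section 10.5 reports: "This yields a total sample size of 122 for a medium effect size" (d = 0.5).

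For the second-stage main effect the section defines the contrast as B+E against C+F among nonresponders. It makes two further assumptions: "We assume nonresponse rates are equal across first-stage treatment assignments", and "an average nonresponse rate of 30% (as informed by prior studies"). It divides 122 by 0.3 to obtain a total of 406, which it then splits as "or N=203 for first-stage treatment groups and 101 in each nonresponse group (B+E and C+F").

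The subgroup table in the Protocol Summary (Subgroup Size and Interventions) gives planned cell sizes. A and D, the responders, have 420 each. B, C, E and F have 90 each; the row for B, for example, reads "Silver diamine fluoride (initial treatment) followed by SDF reapplication plus FV plus electronic toothbrushing".

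Sections 7.1.1 and 10.6.1 send only nonresponders to the second randomization.

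**The concern.** Dividing by 0.3 is meant to find the enrolment at which 30% of children give back the 122 nonresponders that the comparison needs. Those 122 then fall into two groups of 61. The section instead prints 101 per group. Two groups of 101 are 202 nonresponders, half of the 406 children, which contradicts the 30% assumed just before.

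This is the only power-based derivation for the second-stage contrast. Section 10.4.2 places the best sequence for nonresponders among the primary efficacy endpoints, and Section 10.5 sizes the contrast under Objective 1. Its standing is not fully settled, because Sections 3.1 and 10.2 confine the primary objective and the stated hypothesis to the first-stage treatment. Either way, a reader of Section 10.5 would take 101 as the group size that 406 children deliver, or that the design requires, and it is neither.

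**Working it through.** **Inputs.** Two-sided alpha 0.05 (Sections 10.4.1 and 10.5). From Section 10.5: power 0.85, d = 0.5, correlation 0.5, dropout 10%, nonresponse 30% and equal in both first-stage arms. Allocation of 1:1 at the second stage is assumed; the equal cells of 90 in the subgroup table support it.

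**Step 1: the base total of 122.** The protocol does not print its formula. A two-sample t calculation for d = 0.5 needs 72.80 per group. A variance factor of 0.75 is inferred here: both 1 - 0.5² and (1 + 0.5)/2 give it.
- 72.80 x 0.75 = 54.60
- 54.60 / 0.9 = 60.67, rounded up to 61 per group
- 2 x 61 = 122, so the protocol's figure reproduces.

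The normal approximation gives 120. Without the correlation factor the total would be 160, and with a factor of 1 - 0.5 it would be 80; neither matches.

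**Step 2: the enrolled total.** 122 / 0.3 = 406.67. The stated 406 reproduces, rounded down.

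**Step 3: the first-stage arms.** 406 / 2 = 203, which reproduces.

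**Step 4: the pooled second-stage groups.**
- Nonresponders in total: 406 x 0.30 = 121.8
- Per pooled group: 121.8 / 2 = 60.9, about 61
- Stated: 101, which does not reproduce (101 / 61 = 1.66).

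**Where 101 comes from.** 203 / 2 = 101.5, or equally 406 / 4 = 101.5: a quarter of all randomized children, with the 30% never applied.

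**What 101 would require.** Either 202 / 0.3 = 673.3, so 674 children at 30% nonresponse, or a nonresponse rate of 202 / 406 = 49.8% at 406 children. Section 2.1 cites 24% to 36% new caries in earlier school-based trials. At those rates 406 children give 406 x 0.24 / 2 = 48.7 to 406 x 0.36 / 2 = 73.1 per group, so 101 is out of reach across that range too.

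**Cross-check with the subgroup table.** In each trajectory (90 + 90) / (420 + 90 + 90) = 180 / 600 = 30%. Pooled, B+E = C+F = 180 at 1200 children. Scaled to 406: 180 x 406 / 1200 = 60.9. The table applies the 30% rate correctly and agrees with 61.

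**Power** (d = 0.5, factor 0.75, 10% dropout, normal approximation): power = Φ(0.5 / √(2 x 0.75 / n) - 1.96), with n the number per group after dropout.
- 61 per group: n = 54.9, 0.5 / 0.1653 - 1.96 = 1.065, power 86%
- 101 per group: n = 90.9, 0.5 / 0.1285 - 1.96 = 1.932, power 97%

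The 85% target therefore goes with 61, not with 101.

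**The case against.** The strongest reply is that nothing depends on the 101. It ends the derivation and no later section uses it. The inputs and the total of 406 are sound, the correct 61 per group still meets the power target, and enrolment is planned at 1200, about three times 406. All of this stands, and it limits the point to a correction of a stated figure.

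Two stronger readings are tempting, and the documents support neither. A reader might infer that the second-stage contrast has much less information than the protocol claims. That holds only for a hypothetical trial of 406. At 1200 children the subgroup table gives 180 per pooled group, more than the 101. A reader might also infer that 101 would serve as a target for judging whether enough nonresponders have accrued. No section sets such a target: recruitment ends at about 1200 enrolled (Section 5.6).

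It may also be said that 180 in the table and 101 in Section 10.5 belong to different totals and so do not conflict on their face. That is right. The inconsistency appears only after rescaling to 406, as shown above.

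None of this makes 101 correct. Late nonresponders do not rescue it either: under Section 7.1.1, children who become nonresponders after the defined periods stay on their first-stage treatment.

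**Conclusion.** The figure is wrong as written. At 406 children and 30% nonresponse each pooled nonresponse group holds about 61, not 101; the stated value is about two thirds too high. This rests only on the protocol's own 406 and 30% and on 1:1 allocation at the second stage. The inferred variance factor of 0.75 affects the reproduction of 122 and the power figures, but not the 61.

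The required total, the 85% power target for d = 0.5 and the planned enrolment are unaffected. Rounding 406.67 down to 406 instead of up to 407 is trivial. The point is an error in a stated sample size and not a threat to the trial's power.

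**What to change.** In Section 10.5, replace 101 with 61 and say that this is about 122 nonresponders in total. If the total is rounded up in the usual way, write 407 (first-stage arms of 203 and 204). Add that the planned 1200 children give 180 per pooled group before dropout, in line with the 90 shown for each of B, C, E and F in the subgroup table.

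The cost is one corrected sentence. Design, enrolment, randomization and analysis do not change.

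### The >99% power stated for picking out the best of four regimes at effect size 0.1 with N=840 is not supported by the protocol's own inputs

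*Protocol*

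**What the plan says.** Protocol section 10.5 (Sample Size) says of Objective 2: "we estimate power based on the Multiple Comparisons with the Best (MCB) methodology for comparing our embedded DTRs". The error rate is 5%, defined as the chance of wrongly dropping the best regime. Power is computed "assuming the same 10% yearly dropout rate (N=840) for four DTRs, with a minimum effect size of 0.1", with every other regime placed exactly that distance from the best. On dependence it says: "We also assume that correlations between DTRs are equal, in keeping with recommendations". The conclusion is: "This yields a power of >99%, and the study is well powered even for exceedingly small effect size differences". The size of the common correlation, the variances and the scale of the 0.1 are not given.

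Other statements bear on the figure:
- Section 10.5, Objective 1: a total of 122 for Cohen's d = 0.5, power 0.85, alpha 0.05, within-person correlation 0.5. For nonresponse, the authors "further assume an average nonresponse rate of 30% (as informed by prior studies").
- Protocol Summary, table of subgroup sizes: 420/90/90 in each first-stage pathway.
- Section 10.4.3: weighting and replication, with other methods, for the best adaptive intervention. The Statistical Analysis row of the Protocol Summary names augmented inverse probability weighting (AIPW).

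**The concern.** An effect of 0.1 on the Cohen scale is small, and the task described is demanding: all three inferior regimes must be separated from the best. Each regime mean uses only part of one first-stage arm. Power above 99% is hard to square with 840 children, or with the same section's benchmark for a two-group comparison.

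Objective 2 asks for the most effective treatment sequence. Section 3.2 lists it as secondary, but section 10.4.2 also puts the best sequence for nonresponders under primary efficacy. If the stated power stands, a result that fails to separate the regimes could be taken to mean that they hardly differ, when the trial may have had little chance of telling them apart.

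**Working it through.** **1. The plan's own figure.** It cannot be reproduced as stated, because the covariance matrix is missing. Working backwards for 0.1 in SD units, N=840 and equal correlations r, power passes 99% only when r is about 0.93 if N×Var = 2.6 SD² (derived in step 3). If N×Var is as low as 1 SD², r must be about 0.82.

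**2. Cross-check that needs no covariance matrix.** The 122 is roughly recovered as 4 × (1.960 + 1.036)² × 0.75 / 0.25 / 0.9 ≈ 120 (two averaged measures at correlation 0.5, 10% dropout). Required N scales with 1/d²:
- N at d=0.1: 122 × (0.5/0.1)² = 122 × 25 = 3,050 for 85% power.
- Power at 840: Φ(2.996 × √(840/3,050) − 1.960) = Φ(1.572 − 1.960) = 35% two-sided. One-sided: Φ(1.572 − 1.645) = 47%.
- If the dropout allowance is taken out of the 122 (× 0.9 ≈ 110, or 2,745 at d=0.1), two-sided power is about 38%.

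**3. Power under the planned allocation.** Inputs: 1:1 at both stages (implied by 420/90/90), 30% nonresponse, one outcome per child with SD 1, weighting and replication with weights 2 (responders) and 4 (nonresponders).
- N×Var of a regime mean = 2(0.7) + 4(0.3) = 2.6.
- Regimes with the same first stage share responders: covariance 2(0.7) = 1.4, correlation 1.4/2.6 = 0.54. Regimes with different first stages share no children: covariance 0.
- SE of a difference at N=840: across arms √(5.2/840) = 0.079; within an arm √(2.4/840) = 0.053.
- An effect of 0.1 is therefore 1.27 or 1.87 SEs.
- MCB rule: drop regime i if its largest standardized shortfall against any other regime exceeds c, the 95% quantile of that maximum under equal means. Simulation gives c ≈ 2.05.

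Simulated power to drop all three inferior regimes:

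| Effect (SD) | 0.10 | 0.20 | 0.25 | 0.30 | 0.36 |
|---|---|---|---|---|---|
| Power, N=840 | 9% | 58% | 81% | 94% | 99% |

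At 0.1 SD, 80% power needs about N=5,100 and 99% about N=10,800.

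**4. Other assumptions, effect 0.1 SD, N=840 unless noted.**

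| Change from step 3 | Power |
|---|---|
| Nonresponse 20% to 40% | 13% to 7% |
| N=1,200, no dropout | 15% |
| Error rate 10% | 17% |
| Three or six averaged measures, correlation 0.5 | 17% or 20% |
| AIPW, covariates explain 25% or 50% of variance | 14% or 25% |
| AIPW with 50% explained and three averaged measures | about 42% |
| Equal correlation 0 | 6% |
| Equal correlation 0.54 | about 18% |
| Equal correlation 0.54 and six averaged measures | 41% |
| Drop at least one inferior regime instead of all three | 57% |

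The AIPW rows use N×Cov = (1 − R²) × (the step 3 matrix) + R² × (matrix of ones). The cross-arm correlation is then 0.25/2.2 = 0.11 at R² = 0.25 and 0.5/1.8 = 0.28 at R² = 0.5.

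**5. If 0.1 is a 10-point risk difference.** At 30% prevalence the variance is 0.3 × 0.7 = 0.21, so 0.1/√0.21 = 0.22 SD. Power to drop all three is about 67% (58% at 50% prevalence). With AIPW it is 82% at 25% explained and 95% at 50% explained. With 50% explained and three averaged visits it is about 99.5%.

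**The case against.** The strongest objection is to the 9%. It needs four choices that the protocol does not make: 0.1 in SD units, a single outcome per child, no covariate adjustment, and a covariance matrix from plain weighting. The Protocol Summary names AIPW, under which regimes from different arms can be correlated. Section 10.2 evaluates endpoints at visits 3 to 6. The 1:1 ratio is inferred from planned sizes, while section 10.6.1 says adaptive randomization without a ratio. Person-level prevalence is a primary endpoint (section 4.2.1), so a risk-difference reading is possible, and favourable inputs on that reading do reach 99%.

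All of this stands, and it limits what can be said. A reader might infer that the trial has 9% power for Objective 2, or that equal correlation is impossible. The documents support neither: the first depends on unstated inputs, and the second is argued from plain weighting rather than AIPW.

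The stated figure still lacks support. On the SD scale, no plausible combination examined comes near 99%. On the risk-difference scale, reaching 99% takes strong adjustment of a binary outcome plus averaged visits, or a weaker criterion (dropping at least one regime: 99.1% at 30% prevalence). The section mentions none of these, and ten percentage points is not a very small difference.

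**Conclusion.** The power above 99% is unsupported as written. On the only effect-size scale that section 10.5 names, it conflicts with the section's own benchmark, which gives about 35% two-sided for a simpler contrast with the same 840 children. Under plain weighting, each of the two cross-arm regime contrasts is noisier than that whole-arm comparison.

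The best-documented simple case gives about 9%. It assumes 1:1 allocation at both stages, 30% nonresponse, equal variances and one outcome per child. Plausible gains from adjustment, repeated measures or a favourable equal correlation bring it to roughly 15–50%. A 10-point risk difference gives about 67%, more with strong adjustment and averaged visits. The equal correlation needed for 99% on the SD scale, about 0.93 (or 0.82 with unit variance), is far from a design in which regimes with different first stages share no children under weighting and replication.

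It would also go too far to conclude that the trial is too small: the same 840 children give about 81% power at 0.25 SD under the simple weighted estimator.

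**What to change.** In Protocol section 10.5:
1. State the scale of the 0.1 and the outcome that it refers to.
2. State the covariance matrix used: variances and correlations for the planned estimator, with a higher correlation within than across first-stage arms, and any gain assumed from covariates or repeated measures.
3. State whether power means dropping all inferior regimes or at least one.
4. Recompute MCB power at N=840 and replace the single figure with power over a range of effect sizes. Under the simple weighted estimator, with its assumptions written out, the row would be about 9% at 0.1 SD, 58% at 0.2, 81% at 0.25, 94% at 0.3 and 99% near 0.36. If AIPW with repeated measures is the planned analysis, give its figures instead.
5. Delete the statement that the study is well powered for very small differences.

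The cost is one recalculation and a wording change. The stated power becomes less favourable. Enrolment, visits and treatments are unaffected.

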10.6 Measures to Minimize Bias

10.6.1

Enrollment/Randomization/Masking Procedures

BASICS employs a multistage randomization design. In the first stage, participants will be randomized at the individual level to receive either silver diamine fluoride or dental sealants. In the second stage, participants identified as nonresponders will be further randomized at the individual level to each respective adaptive intervention (B, C, E, or F). Randomization will utilize adaptive randomization and be performed by the data collection software provided by New England Survey Systems (NESS).

As this study is a pragmatic trial providing physical interventions, blinding/masking is not possible for the clinical investigators. Additionally, as some interventions create physical changes that are observable (e.g., staining from SDF), patients too cannot be blinded. However, final the final statistical analysis can be masked by recoding of subgroups (See Figure 1).

10.6.2

Evaluation of Success of Blinding

Not applicable.

10.6.3

Breaking the Study Blind/Participant Code

Not applicable.

11 Source Documents and Access to Source Data/Documents

Source data is all information, original records of clinical findings, observations, or other activities in a clinical trial necessary for the reconstruction and evaluation of the trial. Source data are contained in source documents. Examples of these original documents, and data records include: hospital records, clinical and office charts, laboratory notes, memoranda, subjects' diaries or evaluation checklists, pharmacy dispensing records, recorded data from automated instruments, copies or transcriptions certified after verification as being accurate and complete, microfiches, photographic negatives, microfilm or magnetic media, x-rays, subject files, and records kept at the pharmacy, at the laboratories, and at medico-technical departments involved in the clinical trial. It is acceptable to use CRFs as source documents. If this is the case, it should be stated in this section what data will be collected on CRFs and what data will be collected from other sources.

The study case report form (CRF) is the primary data collection instrument for the study. All data requested on the CRF must be recorded. All missing data must be explained. If a space on the CRF is left blank because the procedure was not done or the question was not asked, write "N/D". If the item is not applicable to the individual case, write "N/A". All entries should be printed legibly in black ink. If any entry error has been made, to correct

such an error, draw a single straight line through the incorrect entry and enter the correct data above it. All such changes must be initialed and dated. DO NOT ERASE OR WHITE OUT ERRORS. For clarification of illegible or uncertain entries, print the clarification above the item, then initial and date it.

Access to study records will be limited to IRB-approved members of the study team. The investigator will permit study-related monitoring, audits, and inspections by the IRB/EC, the sponsor, government regulatory bodies, and University compliance and quality assurance groups of all study related documents (e.g. source documents, regulatory documents, data collection instruments, study data etc.). The investigator will ensure the capability for inspections of applicable study-related facilities (e.g. pharmacy, diagnostic laboratory, etc.).

Participation as an investigator in this study implies acceptance of potential inspection by government regulatory authorities and applicable University compliance and quality assurance offices.

12 Quality Assurance and Quality Control

QC procedures will be implemented beginning with the data entry system and data QC checks that will be run on the database will be generated. Any missing data or data anomalies will be communicated to the site(s) for clarification/resolution.

Following written SOPs, the monitors will verify that the clinical trial is conducted and data are generated, documented (recorded), and reported in compliance with the protocol, GCP, and the applicable regulatory requirements (e.g., Good Laboratory Practices (GLP), Good Manufacturing Practices (GMP)).

The investigational site will provide direct access to all trial related sites, source data/documents, and reports for the purpose of monitoring and auditing by the sponsor, and inspection by local and regulatory authorities.

13 Ethics/Protection of Human Subjects

